8.4. Patient Demographics

Baseline characteristics will be summarized for Part C participants. Summaries will include descriptive statistics for continuous and categorical measures. Patient characteristics to be presented include:

- age
- age group: 55 to 64, 65 to 74, and 75 to 86, >86
- gender
- race
- ethnicity
- height
- body weight

- body mass index (weight (kg) / [height (m)]²)
- country
- tobacco use
- alcohol use
- years of education
- work status
- APOE4 carrier status (carrier [ϵ 2/ ϵ 4, ϵ 3/ ϵ 4, ϵ 4/ ϵ 4], noncarrier [ϵ 3/ ϵ 3, ϵ 2/ ϵ 2, ϵ 3/ ϵ 2])
- APOE4 genotype (ϵ 2/ ϵ 4, ϵ 3/ ϵ 4, ϵ 4/ ϵ 4, no ϵ 4)
- having 1 or more first degree relatives with AD
- AChEI and/or memantine use at baseline
- Amyloid PET

8.5. Time Between Clinical, Imaging, and Biomarker Assessments

To better understand the time between feeder study participation and collection of assessments in AACH, weeks between baseline from the feeder study and all subsequent post-baseline assessments will be summarized for the clinical, imaging, and biomarker outcomes.

8.6. Clinical Outcomes

Longitudinal assessment across the feeder study and study AACH will be summarized for Part C participants for ADAS-Cog₁₃, ADCS-iADL, iADRS Total Score, CDR Sum of Boxes, and MMSE Total Score. Change from baseline to each scheduled collection of these measures during the feeder study, to the first on-site assessment from Part A of study AACH, and to the Part C assessment of study AACH will be modelled with an analysis of covariance (ANCOVA) model with factors for baseline score, baseline age, years of education, presence/absence of anti-dementia medications (yes/no), and AACG treatment group.

For comparison purposes to an untreated participant population, change from baseline to each of the same visits will be shown for AACH subjects that participated in Part B of AACH, with the exception that the Part C assessment would be replaced by the Part B Visit 1 (prior to treatment) assessment.

Additionally, each of these outcomes will be analyzed on an annualized basis. Time from the baseline assessment to each post-baseline assessment will be determined and divided by 365 to derive a change per year value. These values will be modelled using the same ANCOVA analysis specified above.

8.7. PET Imaging Outcomes

Longitudinal assessment across the feeder study and study AACH will be summarized for Part C participants for florbetapir PET and flortaucipir PET results. Change from baseline to each scheduled collection of these measures during the feeder study and to the Part C assessment of study AACH will be modelled with an analysis of covariance (ANCOVA) model with factors for baseline PET result, baseline age, years of education, and presence/absence of anti-dementia medications (yes/no).

Additionally, each of these outcomes will be analyzed on an annualized basis. Time from the baseline assessment to each post-baseline assessment will be determined and divided by 365 to derive a change per year value. These values will be modelled using the same ANCOVA analysis specified above.

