Study I5T-MC-AACG (AACG) is an ongoing Phase 2, double-blind, placebo-controlled study to evaluate the safety and efficacy of donanemab in patients with early symptomatic AD.

Study AACG is evaluating approximately 272 patients randomized to donanemab (700 mg Q4W for 3 doses, then 1400 mg Q4W) or placebo.

Study I5T-MC-AACI (AACI) is an ongoing Phase 2, double-blind, placebo-controlled study to evaluate the safety and efficacy of donanemab in patients with early symptomatic AD.

Study AACI is evaluating approximately 500 patients randomized to donanemab (700 mg IV Q4W for 3 doses, then 1400 mg IV Q4W) or placebo.

See the IB for detailed nonclinical, safety, and PK information regarding donanemab.

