#### Part C:

Participants who received donanemab in the originating trial may participate in an imaging and cognitive/functional assessment visit (Visit 201). Visit 201 occurs anytime at least 52 weeks from the participant's last double-blind visit in the originating study.

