For participants in Part C of the study, the interest is whether the changes in brain amyloid deposition, brain tau deposition, and clinical progression of AD for participants who received donanemab in the originating study are maintained after donanemab treatment is removed. For each of these endpoints, change from the last observation of the originating study will be fit using an ANCOVA model including terms for age, years of education, and presence/absence of anti-dementia drugs. Observed case analyses will also be presented.

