8.1. General Considerations

Objectives for Part C of AACH will be addressed with summaries of clinical, imaging, and biomarker data. Data collected from the feeder study from which the participant came, and data from the first on-site visit from Part A will be aggregated with data from Part C to allow for display of longitudinal changes. For comparative purposes, subjects that participate in Part B will also be displayed, with their feeder study, first Part A on-site visit, and Visit 1 from Part B (pre-treatment) aggregated in a similar fashion.

Unless otherwise specified, baseline for clinical, imaging, and biomarker endpoints will be defined as the last observation prior to study drug initiation from the feeder study. When change from baseline is assessed, patients will be included in the analysis only if both a baseline and a Part C measure are available.

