8.8. Plasma Biomarker Outcomes

Longitudinal assessment across the feeder study and study AACH will be summarized for Part C participants for Ptau-217 and neurofilament light chain (NfL) protein. Change from baseline to each scheduled collection of these measures during the feeder study and to the Part C assessment of study AACH will be modelled with an analysis of covariance (ANCOVA) model with factors for baseline value, baseline age, and AACG treatment group. For both of these biomarkers, changes on the original scale and the log-transformed scale will be displayed.

For comparison purposes to an untreated participant population, change from baseline to each of the same visits will be shown for AACH subjects that participated in Part B of AACH, with the exception that the Part C assessment would be replaced by the Part B Visit 1 (prior to treatment) assessment.

Additionally, each of these outcomes will be analyzed on an annualized basis. Time from the baseline assessment to each post-baseline assessment will be determined and divided by 365 to derive a factor to be multiplied by the observed change, resulting in a change per year value. These values will be modelled using the same ANCOVA analysis specified above.

9. References

Mcgraw, Kenneth & Wong, S.P.. (1996). Forming Inferences About Some Intraclass Correlation Coefficients. *Psychological Methods*. 1. 30-46. 10.1037/1082-989X.1.1.30.

10. Appendices

Signature Page for VV-CLIN-076528 v1.0

Approval

PPD

13-Dec-2022 15:02:05 GMT+0000

Signature Page for VV-CLIN-076528 v1.0

Approved on 13 Dec 2022 GMT

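### The additional per-year analysis of Part C florbetapir PET shrinks even when an amyloid reduction is fully maintained, and SAP 8.7 omits the protocol contrast that addresses maintenance

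*SAP*

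**What the plan says.** **Question.** Protocol 9.4.4 asks whether the changes seen in people who received donanemab in the originating study "are maintained after donanemab treatment is removed". For amyloid, tau and clinical progression it specifies an ANCOVA on change from the last originating-study observation.

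**Baseline.** SAP 8.1 uses a different starting point: "baseline for clinical, imaging, and biomarker endpoints will be defined as the last observation prior to study drug initiation from the feeder study". This agrees with the Part C endpoint in the protocol objectives table, which is also change from originating-study baseline.

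**PET analysis.** SAP 8.7 first plans raw change from that baseline to each feeder-study scan "and to the Part C assessment of study AACH will be modelled with an analysis of covariance (ANCOVA) model". It then continues: "Additionally, each of these outcomes will be analyzed on an annualized basis". The annualising rule is "Time from the baseline assessment to each post-baseline assessment will be determined and divided by 365 to derive a change per year value", and the same ANCOVA is applied to the result. The covariates are baseline PET, age, education and anti-dementia medication; there is no term for elapsed time.

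**Timing.** Protocol 4.1, under Part C: "Visit 201 occurs anytime at least 52 weeks from" the last double-blind visit. No upper limit is given, and no drug is given in Part C.

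**Plasma markers.** SAP 8.8 repeats the plan ("each of these outcomes will be analyzed on an annualized basis") but describes the calculation differently: time divided by 365 becomes a multiplier for the observed change.

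**The concern.** A per-year rate is a fair summary when change accrues at a roughly constant pace from the start of the clock. The protocol describes amyloid differently. In AACC (protocol 2.2.3.1) there was a mean reduction of 50% among patients given 3 to 5 doses at the highest dose level, and protocol 4.3 reports large reductions after a single dose. For Part C participants the plausible path is a fall during the feeder study followed by at least a year without drug.

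Dividing the whole change by the whole elapsed time spreads the on-treatment fall over the off-treatment period. The per-year value at Visit 201 must then be smaller than at the last feeder scan, even if no plaque has returned, and smaller again for people seen later. Anyone setting these per-year values side by side could take arithmetic shrinkage for loss of effect, on the very question Part C was set up to explore. Annualising is normally meant to remove dependence on visit timing. Here it creates it.

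**Working it through.** **Inputs**

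- Start of the clock: pre-treatment feeder baseline (SAP 8.1).
- g, time from last feeder scan to Visit 201: about 52 weeks or more, with no maximum (protocol 4.1), taking the last feeder scan as no later than the last double-blind visit.
- T, time from feeder baseline to last feeder scan: not stated for AACG or AACI. Protocol 2.2.3.1 gives design and size only ("Study AACG is evaluating approximately 272 patients randomized to donanemab", with a placebo group). T is therefore an assumption, shown over a range. Two figures in the same section help to frame it: dosing of up to 72 weeks in AACD, and about 7 months between scans in AACC, which is 7 × (365/12)/7 = 30.4 weeks. The SAP revision history names AACC as a feeder study.
- The plan gives no figure of its own to reproduce.

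**Formula.** Read the rule as change divided by (days/365). Let D be a reduction reached at T and fully held to T+g.

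- Per-year value at last feeder scan: D / (7T/365)
- Per-year value at Visit 201: D / (7(T+g)/365)
- Ratio: T/(T+g). Apparent loss: g/(T+g), whatever the size of D.

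**Worked case.** D = −100 (arbitrary units), T = 72, g = 52.

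- Feeder: −100/(504/365) = −72.4 per year
- Visit 201: −100/(868/365) = −42.1 per year
- Apparent loss: 52/124 = 41.9%, with true loss zero

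| T (weeks) | g (weeks) | g/(T+g) | Apparent loss |
|---|---|---|---|
| 76 | 52 | 52/128 | 40.6% |
| 72 | 52 | 52/124 | 41.9% |
| 72 | 78 | 78/150 | 52.0% |
| 72 | 104 | 104/176 | 59.1% |
| 72 | 130 | 130/202 | 64.4% |
| 52 | 52 | 52/104 | 50.0% |
| 52 | 78 | 78/130 | 60.0% |
| 30.4 | 52 | 52/82.4 | 63.1% |

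At the minimum gap of 52 weeks, the loss is at least 40% for any T up to 78 weeks, and falls below 25% only if T exceeds 156 weeks.

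**Across participants.** Take two people with T = 72 and the same maintained change of −100, one seen at g = 52 and one at g = 104. Their per-year values are −42.1 and −29.6. The second is about 30% smaller (124/176 = 0.70) solely because of the later visit.

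**What the other contrasts show.** Under full maintenance, raw change from baseline has a Visit 201 to last-feeder ratio of 1.00, and change from the last originating-study scan is 0. A simulation with T = 72, g uniform on 52 to 104 weeks and a mean reduction of about 80 units agreed: raw ratio 1.00, mean off-treatment change −0.04 units, and annualised apparent loss 51.5%.

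**Formula wording.** SAP 8.6 and 8.7 divide time by 365 and do not say how the change enters. Taken literally, SAP 8.8 multiplies change by years. At T = 72, g = 52, that would make a maintained change look larger at the late visit by (T+g)/T = 124/72 = 1.72, an error in the opposite direction.

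**The case against.** The strongest reply is that the annualised analysis is a supplement. The same section first models raw change to each feeder scan and to Visit 201, which under full maintenance shows no loss. SAP 8.5 also summarises the elapsed times, so the changing denominator is visible. Nothing in SAP 8.7 says that per-year values will be compared across visits to judge maintenance, and Part C is exploratory with no decision attached. All of this stands, and it limits the point to one additional output.

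A reader might infer that the planned PET results would make a maintained reduction look 40% to 60% lost. The documents do not support that. The raw-change analysis would show the reduction held, and the range appears in neither document. It depends on assumed T and g and is not a bound: the AACC scan interval gives at least 63%, and a long enough gap exceeds 60% at T = 72.

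A reader might also extend the argument to tau PET and the plasma markers. The documents do not establish a fall-then-plateau path for those. Protocol 8.8 describes tau deposits as accumulating with disease progression, and for a steadily accumulating measure with variable visit timing, annualising is reasonable.

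The reply leaves two things unanswered. The per-year change from pre-treatment baseline cannot address maintenance of amyloid removal. And the raw change in SAP 8.7 allows the off-treatment change to be read off only indirectly, because the direct contrast in protocol 9.4.4 was not carried over.

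**Conclusion.** The point holds for the additional annualised florbetapir analysis at Visit 201. With a fully maintained reduction, the per-year value is smaller than at the last feeder scan by g/(T+g): about 42% at T = 72 and g = 52, 50% at 52 and 52, 60% at 52 and 78, and 63% at about 30 and 52. It grows with later visits. The formula follows from the SAP's own baseline and clock. The percentages rest on assumed T, on g of 52 weeks or more, on complete maintenance, and on reading the rule as change divided by years. The distortion is limited to annualised values compared across visits or across participants with different gaps. Separately, SAP 8.7 lacks the protocol 9.4.4 contrast, and the annualising formula is incomplete in SAP 8.6 and 8.7 and, taken literally, wrong in SAP 8.8. As an exploratory matter this is a modest defect, but it bears directly on the Part C question and is cheap to correct.

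**What to change.** 1. In SAP 8.7, for florbetapir, add change from the last originating-study scan to Visit 201, using the ANCOVA in protocol 9.4.4. If a rate is wanted, annualise this change over that off-treatment interval only.
2. Drop the per-year change from pre-treatment baseline at Visit 201 for florbetapir, or label it as not evidence on maintenance. Keep the raw change from baseline as planned.
3. In SAP 8.6 to 8.8, write the annualised value explicitly as change divided by (days from start to end of the interval / 365), and remove the multiplier wording from SAP 8.8.

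The cost is a SAP edit and a little extra analysis. No new data are needed. The added contrast is limited to participants with an originating-study scan.

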8.8. Plasma Biomarker Outcomes

Longitudinal assessment across the feeder study and study AACH will be summarized for Part C participants for Ptau-217 and neurofilament light chain (NfL) protein. Change from baseline to each scheduled collection of these measures during the feeder study and to the Part C assessment of study AACH will be modelled with an analysis of covariance (ANCOVA) model with factors for baseline value, baseline age, and AACG treatment group. For both of these biomarkers, changes on the original scale and the log-transformed scale will be displayed.

For comparison purposes to an untreated participant population, change from baseline to each of the same visits will be shown for AACH subjects that participated in Part B of AACH, with the exception that the Part C assessment would be replaced by the Part B Visit 1 (prior to treatment) assessment.

Additionally, each of these outcomes will be analyzed on an annualized basis. Time from the baseline assessment to each post-baseline assessment will be determined and divided by 365 to derive a factor to be multiplied by the observed change, resulting in a change per year value. These values will be modelled using the same ANCOVA analysis specified above.

9. References

Mcgraw, Kenneth & Wong, S.P.. (1996). Forming Inferences About Some Intraclass Correlation Coefficients. *Psychological Methods*. 1. 30-46. 10.1037/1082-989X.1.1.30.

10. Appendices

Signature Page for VV-CLIN-076528 v1.0

Approval

PPD

13-Dec-2022 15:02:05 GMT+0000

Signature Page for VV-CLIN-076528 v1.0

Approved on 13 Dec 2022 GMT

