## Part C

	Part C	Comments
Visit Number	201	
Timing	Any time $\geq$ 52 weeks after participant's last double-blind visit in the originating study.	Procedures may take more than 1 day.
PET Scans		
Flortaucipir F 18 PET scan	X g	
Florbetapir F 18 PET scan	X g	
Clinician Administered Assessments (Electronic)		
ADAS-Cog 13	X	If a PET scan is done on the same day, administer the ADAS-Cog 13 , ADCS-ADL, CDR-SB, and MMSE prior to PET scan. These tests include the audio voice recording of the rater's questions and the participant and study partner responses to assessment questions.
ADCS-ADL	X	
CDR-SB (Global Sum of Boxes - CDR)	X	
MMSE	X	
P-tau	X	
NfL	X	
A $\beta$	X	
Exploratory biomarker samples	X	Collect unless not allowed or unfeasible due to local regulations.
AEs	X	
Concomitant medications	X	

Abbreviations: A $\beta$  = amyloid beta; ADA = antidrug antibody; ADAS-Cog13 = Alzheimer's Disease Assessment Scale – Cognitive subscale; ADCS-ADL = Alzheimer's Disease Cooperative Study – Activities of Daily Living Inventory; AE = adverse event; BP = blood pressure; CDR-SB = Clinical Dementia Rating Scale – Sum of Boxes; C-SSRS = Columbia Suicide Severity Rating Scale; CRF = case report form; ECG = electrocardiogram; ED = early discontinuation; IP = investigational product; IV = intravenous; IWRS = interactive web-response system; MMSE = Mini Mental State Examination; MRI = magnetic resonance imaging; NfL = neurofilament light chain; PET = positron emission tomography; PK = pharmacokinetics; P-tau = phosphorylated tau; UP = unscheduled procedure; UV = unscheduled visit; V = visit.

- a V601 occurs up to 30 days prior to V602. V602 cannot occur <30 days from the participant's last double-blind visit of the originating study. V602 through V607 each occur 4 weeks apart. Part A visits may occur up to 24 weeks prior to Part B (V1), for eligible participants. The exact week relative to V1 depends on the number of PAIRs in which the participant elects to participate. The time between the final visit of Part A and the first visit of Part B or Part C is  $\geq$ 4 weeks.
- b UP takes place at the start of Part B (prior to V1), and is only conducted if: participant's last MRI from the originating study is >12 months from V1, or last labs from the originating study were collected >6 months from V1. The investigator confirms continued eligibility as described in Section [7.2](#).

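### SAP 8.8 multiplies the plasma-biomarker change by years elapsed instead of dividing by it, so the annualised Ptau-217 and NfL values are wrong by a factor of t squared if programmed as written

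*SAP*

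**What the plan says.** SAP Section 8.8 covers longitudinal plasma biomarkers, "summarized for Part C participants for Ptau-217 and neurofilament light chain (NfL) protein". Change from the feeder-study baseline to each feeder visit and to the Part C assessment is analysed by an ANCOVA "model with factors for baseline value, baseline age, and AACG treatment group". For both biomarkers, "changes on the original scale and the log-transformed scale will be displayed".

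The section then adds an annualised analysis. Its starting quantity is elapsed time: "Time from the baseline assessment to each post-baseline assessment will be determined and divided by 365". The quotient is used in this way: "divided by 365 to derive a factor to be multiplied by the observed change, resulting in a change per year value". The resulting values go into the same ANCOVA.

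Three other places bear on how elapsed time varies:

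- Protocol Section 4.1, Part C: "Visit 201 occurs anytime at least 52 weeks from the" last double-blind visit of the originating study. No latest date is given.
- Protocol Section 1.3, Schedule of Activities, footnote a: "The time between the final visit of Part A and the first visit of Part B or Part C is" at least 4 weeks. This matters because SAP 8.8 substitutes Part B Visit 1 for the Part C assessment in the untreated comparison group.
- SAP Section 8.5: "weeks between baseline from the feeder study and all subsequent post-baseline assessments will be summarized". This is a descriptive summary and adjusts nothing.

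SAP Sections 8.6 and 8.7 also divide time by 365 and call the result a yearly change, but they do not say how the observed change enters the calculation. Only 8.8 spells out a multiplication.

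**The concern.** The rule cannot produce the quantity it names. Multiplying a change by years gives units of change times years, whereas a yearly rate needs division. No other formula in the SAP or protocol corrects this.

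The error is not a constant rescaling that would cancel in comparisons. Its size depends on each participant's own follow-up time. Visit 201 has a minimum but no maximum, and in the comparison group it is replaced by a visit with a different minimum. With no time term in the model, annualisation is the only adjustment for follow-up time in 8.8, and the written rule pushes it the wrong way. Within one participant, feeder visits before one year would be understated and Part C overstated, which distorts the longitudinal display.

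Because the instruction is explicit, independent double programming against the SAP could reproduce the error rather than expose it.

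**Working it through.** The plan gives no numerical figure on this point, so there is nothing to reproduce. The check is algebra with illustrative numbers.

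**Inputs**

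- t = days from baseline / 365 (SAP 8.8). Baseline is the last feeder-study observation before study drug (SAP 8.1).
- Earliest Visit 201: 52 × 7 = 364 days after the last double-blind visit (Protocol 4.1).
- Earliest Part B Visit 1, ignoring the ±4-day visit tolerance: 30 days to Visit 602, 28 to Visit 603 and 28 to Visit 1, or 86 days after the last double-blind visit (Protocol 1.3, footnote a).
- Length of the feeder double-blind period: not in the documents. I assume 24, 52 or 76 weeks to show a range.

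**Step 1: the ratio.** For an observed change d, the written value is d × t and the correct value is d / t. Written / correct = t².

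**Step 2: error at a given time from baseline**

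| Weeks from baseline | t | Written / correct (t²) |
|---|---|---|
| 24 | 0.460 | 0.21 |
| 52 | 0.997 | 0.99 |
| 76 | 1.458 | 2.12 |
| 104 | 1.995 | 3.98 |
| 128 | 2.455 | 6.03 |

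For example, a change of 1 unit over 128 weeks is 1 / 2.455 = 0.407 per year. The written rule reports 2.455.

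**Step 3: earliest Visit 201**

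| Assumed feeder length | Days from baseline | t² |
|---|---|---|
| 24 weeks | 168 + 364 = 532 | 2.12 |
| 52 weeks | 364 + 364 = 728 | 3.98 |
| 76 weeks | 532 + 364 = 896 | 6.03 |

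Whatever the feeder length, t exceeds 1 at Visit 201 once baseline to last double-blind visit is longer than 365 − 364 = 1 day.

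**Step 4: sensitivity to follow-up time, with no timing assumption.** Take two participants with the same constant yearly rate r. The observed change is r × t, the correct annualised value is r, and the written value is r × t².

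| Second participant followed | Correct | Not annualised | As written |
|---|---|---|---|
| 10% longer | 0% difference | 10% | 1.10² − 1 = 21% |
| 20% longer | 0% difference | 20% | 1.20² − 1 = 44% |

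For comparing participants with unequal follow-up, the written rule is worse than not annualising at all.

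**Step 5: group contrast, illustration only.** Put both groups at their earliest dates with equal true rates.

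| Assumed feeder length | Days, Part C / Part B Visit 1 | Not annualised | As written |
|---|---|---|---|
| 24 weeks | 532 / 254 | 2.09-fold | 2.09² = 4.39-fold |
| 76 weeks | 896 / 618 | 1.45-fold | 1.45² = 2.10-fold |

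The correct formula shows no difference in either row. The contrast also vanishes if follow-up times are equal, and it reverses if Visit 1 comes later than Visit 201.

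**The case against.** The best defence is that this is a drafting slip. The sentence names its target as a yearly change, and only 365/days gives that. A statistician programming it should see that the units fail, and nothing shows it was coded literally. Sections 8.6 and 8.7 are loosely worded too, which suggests shorthand for ordinary annualisation throughout. All of this stands as a limit on the practical harm. It does not make the rule correct: 8.8 goes beyond its sister sections by naming a factor and a multiplication.

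The objections to size also have some force:

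- The group contrast in Step 5 puts both groups at minimum dates. The protocol itself provides for Visit 1 falling more than 12 months after the last feeder MRI, so those dates may be untypical. Part of the contrast is a timing difference that is present without annualising, as the table shows.
- Part B Visit 1 is bounded relative to study entry, because screening is limited to 30 days and Part A to 24 weeks. The gap from the last double-blind visit to entry has no cap, however, so time from feeder baseline remains open-ended.
- SAP 8.8 says the comparison group's changes will be shown. It does not state outright that those participants enter the annualised ANCOVA, although the treatment-group factor makes that plausible.

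Finally, the consequence is limited. The sign of each change is preserved, the unannualised ANCOVA is reported alongside, and no primary or secondary endpoint is touched.

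**Conclusion.** The concern holds. As written, the annualised Ptau-217 and NfL values equal the true yearly change times t². At the earliest Visit 201 that is an overstatement of 2.1, 4.0 or 6.0 times under assumed feeder periods of 24, 52 or 76 weeks, and more for later visits. The t² result needs no assumption; the multiples depend on the feeder length. Which group, if either, would be favoured depends on actual visit dates and cannot be determined from the documents. At a fixed feeder visit, where t is nearly the same for everyone, mainly the reported scale is wrong.

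This should be fixed, but its reach is narrow: a supplementary analysis of exploratory Part C biomarkers, and only if the sentence is implemented literally. Confidence in the algebra is high. The documents do not show whether the code follows the wording.

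**What to change.** Replace the sentence in SAP 8.8 with an explicit formula: annualised change = observed change / (days from baseline / 365), which is the same as observed change × 365 / days. State that it applies to both the original-scale and the log-scale change. Check any existing program against it and rerun the annualised tables if it was coded as written.

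As a separate clarification, put the same formula in 8.6 and 8.7, where the role of the observed change is left unstated.

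The cost is one sentence in 8.8, a code check and an optional sentence in each of the other two sections. No design, data-collection or sample-size change is involved.
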